## 11.0 STUDY MANAGEMENT

### 11.1 Institutional Review Board (IRB) Approval and Consent

It is expected that the IRB will have the proper representation and function in accordance with federally mandated regulations. The IRB should approve the consent form and protocol.

In obtaining and documenting informed consent, the investigator should comply with the applicable regulatory requirement(s), and should adhere to Good Clinical Practice (GCP) and to ethical principles that have their origin in the Declaration of Helsinki.

Before recruitment and enrollment onto this study, the patient will be given a full explanation of the study and will be given the opportunity to review the consent form. Each consent form must include all the relevant elements currently required by the FDA Regulations and local or state regulations. Once this essential information has been provided to the patient and the investigator is assured that the patient understands the implications of participating in the study, the patient will be asked to give consent to participate in the study by signing an IRB-approved consent form.

Prior to a patient's participation in the trial, the written informed consent form should be signed and personally dated by the patient and by the person who conducted the informed consent discussion.

## **11.2 Required Documentation**

Before the study can be initiated at any site, the following documentation must be provided to the Study Sponsor.

- A copy of the official IRB approval letter for the protocol and informed consent
- IRB membership list
- CVs and medical licensure for the principal investigator and any associate investigators who will be involved in the study
- A copy of the IRB-approved consent form
- Executed clinical research contract (if applicable)

The above documentation will be provided to our Study Sponsor (LCCC).

## **11.3 Registration Procedures**

Patients will be registered into OnCore®, a web based clinical research platform by one of the Study Coordinators. The spread sheet contains each subject enrolled in the study identified by the patient first and last initial, study id, date of enrollment into study, race and ethnicity.

## **11.4 Data Management and Monitoring/Auditing**

The breast images of all eligible enrolled subjects that are obtained and contribute to the ultimate diagnosis leading to biopsy will be de-identified for inclusion in the reader study. Copies of the clinical report forms as well as the de-identified images described in the preceding will be submitted for each case to the Study Coordinators for maintaining the study record and entering the data into a spreadsheet in preparation for the reader study.

As an investigator initiated study, this trial may also be audited by the Lineberger Cancer Center audit committee every twelve months.

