#### 1.3.1 **Screening Based on Angiogenesis-Acoustic Angiography**

Acoustic angiography allows for the viewing of vessel shape and delineation of 'tortuosity,' which can indicate the presence and progression of cancer. This ability to image the microvasculature depends on the use of a multi (high) frequency ultrasound scanner in addition to a traditional single-frequency pulse-echo ultrasound scanner (b-mode ultrasound), the latter to ensure accurate anatomical location of the lesion. Because of this dependence on pulse-echo, the technique is referred to as "acoustic" angiography [62].

Acoustic angiography also depends on use of an ultrasound contrast agent. Contrast enhanced ultrasound imaging has been used for nearly two decades for clinical cardiology in the United States (and is currently routinely used in UNC Hospital Cardiology Clinics), and is much more widely used in Europe and Asia for visualization of blood perfusion in organs, tissues, and tumors.[51] Early concerns about the safety of ultrasound contrast (specifically with the contrast agent (perflutren lipid; Definity®) due to events in a clinical trial have been resolved; the overwhelming amount of more recent evidence from large clinical studies has shown that contrast ultrasound is very safe.[52-54] In fact ,it is much safer than other commonly used techniques, such as coronary angiography, exercise ECG, or myocardial scintigraphy.[55] Furthermore,

it does not have the risks of nephrogenic systemic fibrosis associated with gadolinium based MRI contrast agents when used in renally compromised patients. On October 27, 2011, the FDA eliminated the requirement for patient monitoring 30 minutes after ultrasound contrast examination, based on these and other recent safety data. The ultrasound contrast agent to be used in LCCC1405 is perflutren lipid.

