**1.5 Rationale**

One main limitation to the widespread use of contrast enhanced ultrasound clinically has been the lack of availability of state-of-the art contrast imaging approaches available to clinicians. However, contrast ultrasound will likely become far more widespread as new imaging techniques, such as acoustic angiography, demonstrate their usefulness and become available on commercial ultrasound systems. We propose to evaluate a novel ultrasound method that could potentially improve the sensitivity and specificity of traditional breast ultrasound. Increasing the accuracy of diagnostic imaging in high risk patients could provide substantial clinical benefit by improving diagnosis, preventing over-treatment, and reducing healthcare costs.

LCCC1405 is designed to compare the sensitivity and specificity of contrast enhanced ultrasound (acoustic angiography) to the sensitivity and specificity of conventional ultrasound in women scheduled to undergo a biopsy based on pre-study imaging results. The gold standard for sensitivity and specificity, then, will be based on pathological results. The Breast Imaging Reporting and Data System (BIRADS) is used by radiologists who read mammograms, ultrasounds and MRIs to indicate their level of suspicion of the possibility of breast cancer. Scores range from 0 to 6, with scores of 4-5 indicating suspicious results, while 6 indicates an existing diagnosis of breast cancer. This study is limited to women with a score of 4-5 based on pre-study imaging.

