## 4.0 STUDY PLAN

#### 4.1 Schema

This is a one arm single center study of 60 patients with suspicious breast lesions (BIRADS 4 or 5) from the UNC Breast Clinic that consent to undergo an acoustic angiography in conjunction with b-mode ultrasound prior to their scheduled biopsy.

 Pre-ultrasound contrast agent  
 Based on results of pre-study imaging

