#### **4.3.2 Acoustic Angiography Imaging Procedures**

Acoustic angiography imaging involves a research high frequency ultrasound scanner (VisualSonics Vevo 770; see section 5.0) in contrast imaging mode. In addition, we may use a standard FDA-approved clinical ultrasound system to obtain a second conventional B-mode ultrasound image as a gold standard. Imaging will be performed within the package insert guidelines for ultrasound system mechanical index (a measurement of output power) when imaging perflutren contrast agent (less than 0.8).

Acoustic angiography imaging will be performed by a trained medical personnel using mild compression to eliminate motion. A linear translation stage will be attached to the transducer to mechanically translate the

transducer the imaging distance (up to approximately 3 cm). Total imaging time per pass is estimated to be 60 seconds, similar to a standard ultrasonography exam. All image data will be de-identified and transferred for off-line analysis based on a study ID. The research images will NOT be interpreted or analyzed for clinical decisions related to the patient. See section 5.0 for additional information on the acoustic angiography device.

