#### 4.4 Standard of Care Biopsy

The patient will then undergo her scheduled breast biopsy procedure based on the pre-study diagnostic imaging. The research acoustic angiography imaging will NOT be interpreted prior to the breast biopsy and therefore will not influence any clinical decision concerning the biopsy.

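### Section 11.4 conflicts with 4.1, 4.3.2 and 4.6 over the reader-study images, and the surviving text leaves open which b-mode acquisition is scored for the primary endpoint

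*Combined protocol and SAP*

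**What the plan says.** On what enters the reader study, 11.4 (Data Management and Monitoring/Auditing) states that the "breast images of all eligible enrolled subjects that are obtained and contribute to the ultimate diagnosis leading to biopsy will be de-identified for inclusion". Section 4.6 gives the five readers a different set: whatever is imaged under the study, scored as acoustic angiography against conventional b-mode.

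On what led to biopsy, 4.4 says that the procedure follows from the pre-study diagnostic imaging and that "The research acoustic angiography imaging will NOT be interpreted prior to the breast biopsy". Inclusion criterion 3.1.2 requires BI-RADS 4 or 5 on pre-study standard-of-care imaging without naming a modality, and 1.5 notes that BI-RADS "is used by radiologists who read mammograms, ultrasounds and MRIs".

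On the b-mode scan itself:
- 4.1 describes patients who "consent to undergo an acoustic angiography in conjunction with b-mode ultrasound prior to their scheduled biopsy". A surviving schema footnote reads "Pre-ultrasound contrast agent".
- 1.3.1 says that the high-frequency scanner is used "in addition to a traditional single-frequency pulse-echo ultrasound scanner (b-mode ultrasound), the latter to ensure accurate anatomical location of the lesion".
- 4.3.2 says that "we may use a standard FDA-approved clinical ultrasound system to obtain a second conventional B-mode ultrasound image as a gold standard".

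On the reference standard, 1.5 states: "The gold standard for sensitivity and specificity, then, will be based on pathological results". Sections 2.3 and 10.0 agree that it is pathology.

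The primary analysis in 10.2.1 estimates sensitivity and specificity for both modalities and their differences. It calls the comparator only b-mode ultrasound. The Appendix A form calls it only ULTRASOUND.

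**The concern.** Half of the primary comparison depends on the b-mode image, and the sections point to different images. Section 11.4 is an operational instruction about which images staff de-identify and submit for reading, and 11.5 requires the study to be run as written. If staff follow 11.4, readers score as comparator an image that helped put the lesion into the study, and for some patients that image may not be ultrasound at all. If staff follow 4.1 and 4.6, readers score a scan made at the study visit. If the optional scan in 4.3.2 is also made, a patient may have two study-visit b-mode images and no rule for choosing between them.

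The choice is not neutral. Every enrolled lesion was already judged suspicious on pre-study imaging. Scoring that same image ties the comparator to the selection; acoustic angiography played no part in it. Leaving the choice open until reading starts also allows it to be made image by image.

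**Working it through.** **1. The plan's own power figure.** Inputs from 10.1: about 30 benign lesions (half of 60), 5 readers, within-patient correlation 0.5, specificity 70% under the null and 90% under the alternative, one-sided 0.05.

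- Effective n = 30 × 5 / (1 + 4 × 0.5) = 50.
- Power = Φ[(0.20 − 1.645 × √(0.70 × 0.30/50)) / √(0.90 × 0.10/50)] = Φ[(0.20 − 0.1066) / 0.0424] = Φ(2.20) = 98.6%, against 98% stated.
- The same formula gives 96.3% with 25 benign lesions (stated as above 96%) and 72.3% with 13 (stated 72%).

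The sample-size statement reproduces. It does not depend on which b-mode image is scored, because it tests against a fixed 70%.

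**2. The candidate comparators side by side.**

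| Candidate | Source | Secured as b-mode in every patient? | Helped select the lesion? |
|---|---|---|---|
| Image that led to biopsy | 11.4 read with 4.4 and 3.1.2 | No; modality not restricted | Yes |
| B-mode at the study visit with acoustic angiography | 4.1 and its footnote; 1.3.1 | Implied, not stated as the scored image | No |
| Optional b-mode on a clinical system | 4.3.2 | No; it may be obtained | No |

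The word second in 4.3.2 can mean second to a study-visit scan or second to the pre-study scan. On the latter reading, the scan that 4.1 treats as part of the study would be the one that 4.3.2 makes optional. Sections 2.1, 2.3, 4.6, 10.0 and 10.2.1 and Appendix A do not separate the candidates.

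**3. Direction of the effect.** Take benign lesions only. Let S be a reader's specificity on b-mode before any selection, c the clinical false-positive rate, and a the correlation between the clinical suspicious call and the reader's malignant call. For a lesion selected on that call,

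P(reader says not malignant | clinically suspicious, benign) = S − a × √(S(1 − S)(1 − c)/c).

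This is below S whenever a is positive, and it falls as a rises. Reading the very image behind the clinical call should give a larger a than reading a fresh scan; that is an assumption, though a mild one. The effect reaches only lesions referred on ultrasound. The same reasoning applied to malignant lesions raises b-mode sensitivity, so the two halves of the endpoint would move in opposite directions. Section 10.1 names specificity as the primary interest.

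**4. Size.** The documents give no value for a, for c in this clinic, or for the share of lesions referred on ultrasound. No figure for the shift can be derived from them.

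**The case against.** The strongest reply is that the intent is plain. Section 11.4 says neither only nor pre-study; the link to pre-study imaging comes through 4.4. Research images have their own route in 4.3.2, which de-identifies them and transfers them for off-line analysis. Section 4.6, on its natural reading, covers study imaging and not pre-study imaging. The schema footnotes treat the pre-contrast state and the pre-study imaging results as separate items, so the missing figure may show a pre-contrast study-visit b-mode as the comparator.

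Much of this stands. A reader might infer from 11.4 that acoustic angiography would be left out of the reader study. The documents do not support that: 4.3.2, 4.6, 10.2.1 and the form all show that it is to be read and scored. Nor can one say that the schema fails to identify the b-mode image, since it is not available here.

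The reply does not dispose of the conflict. Intent does not tell staff which scan to load, or which to use when two exist. Even if the schema names the image, 11.4 and 4.3.2 would have to be brought into line with it.

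**Conclusion.** The conflict is real and should be corrected before any reading begins. Section 11.4 names an image set that 4.1 and 4.6 contradict, 4.3.2 adds an optional image with a label that belongs to pathology, and the surviving text does not say which b-mode acquisition is scored. If 11.4 is followed, b-mode specificity can be lowered relative to a fresh scan, in favour of acoustic angiography. This rests on two assumptions: that some lesions were referred on ultrasound, and that re-reading the triggering image agrees more closely with the clinical call than reading a new one. The size is not fixed by the documents.

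Two further inferences are tempting and should not be drawn. The stated power is not wrong; it reproduces. Nor does this point undermine the 70% in 10.1, which is a planning value that the protocol intends to check in the trial, while 10.2.1 already plans the in-study difference.

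**What to change.** - **11.4:** state that the reader study uses the acoustic angiography images and one named b-mode acquisition, giving scanner and timing, fixed before reading starts. The study-visit, pre-contrast b-mode that 4.1 and its footnote point to is the natural choice. State that the images that triggered biopsy are not the scored comparator.
- **4.3.2:** say whether the clinical-system image is that comparator, in which case it is obtained in every patient, or only an extra image. Delete the gold-standard label.
- **4.6 and Appendix A:** use the same name for the comparator, replacing ULTRASOUND on the form. Check that the schema in 4.1 agrees.

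The cost is wording in a few sections and a form label, and possibly a short b-mode scan where none is already done; 5.2 describes one visit with 15 minutes of imaging. A re-acquired image reduces the selection effect but does not remove it, because the lesions were still enrolled as suspicious.

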## **11.5 Adherence to the Protocol**

Except for an emergency situation in which proper care for the protection, safety, and well-being of the study patient requires alternative treatment, the study shall be conducted exactly as described in the approved protocol.

### **11.5.1 Emergency Modifications**

UNC investigators may implement a deviation from, or a change of, the protocol to eliminate an immediate hazard(s) to trial subjects without prior UNC IRB approval.

For any such emergency modification implemented, a UNC IRB modification form must be completed by UNC Research Personnel within five (5) business days of making the change.

### 11.5.2 Single Patient/Subject Exceptions

Any request to enroll a single subject who does not meet all the eligibility criteria of this study requires the approval of the UNC Principal Investigator and the UNC IRB.

### 11.5.3 Other Protocol Deviations/Violations

All other planned deviations from the protocol must have prior approval by the Principal Investigator and the UNC IRB. According to UNC's IRB, a protocol deviation is any unplanned variance from an IRB approved protocol that:

- Is generally noted or recognized after it occurs
- Has no substantive effect on the risks to research participants
- Has no substantive effect on the scientific integrity of the research plan or the value of the data collected
- Did not result from willful or knowing misconduct on the part of the investigator(s).

An unplanned protocol variance is considered a violation if the variance:

- Has harmed or increased the risk of harm to one or more research participants.
- Has damaged the scientific integrity of the data collected for the study.
- Results from willful or knowing misconduct on the part of the investigator(s).
- Demonstrates serious or continuing noncompliance with federal regulations, State laws, or University policies.

If a deviation or violation occurs without prior approval from the Principal Investigator, please follow the guidelines below:

**Protocol Deviations:** UNC personnel will keep a log of any protocol deviations and report them to the study sponsor or data and safety monitoring committee in accordance with their policies. Deviations should be summarized and reported to the IRB at the time of continuing review.

**Protocol Violations:** Violations should be reported by UNC personnel within one (1) week of the investigator becoming aware of the event using the same IRB online mechanism used to report Unanticipated Problems.

### 11.6 Amendments to the Protocol

Should amendments to the protocol be required, the amendments will be originated and documented by the Principal Investigator at UNC. It should

also be noted that when an amendment to the protocol substantially alters the study design or the potential risk to the patient, a revised consent form might be required.

The written amendment, and if required the amended consent form, must be sent to UNC's IRB for approval prior to implementation.

### **11.7 Record Retention**

Study documentation includes all Case Report Forms, data correction forms or queries, source documents, Sponsor-Investigator correspondence, monitoring logs/letters, and regulatory documents (e.g., protocol and amendments, IRB correspondence and approval, signed patient consent forms).

Source documents include all recordings of observations or notations of clinical activities and all reports and records necessary for the evaluation and reconstruction of the clinical research study.

Government agency regulations and directives require that all study documentation pertaining to the conduct of a clinical trial must be retained by the study investigator. In the case of a study with a drug seeking regulatory approval and marketing, these documents shall be retained for at least two years after the last approval of marketing application in an International Conference on Harmonization (ICH) region. In all other cases, study documents should be kept on file until three years after the completion and final study report of this investigational study.

### **11.8 Obligations of Investigators**

The Principal Investigator is responsible for the conduct of the clinical trial at the site in accordance with Title 21 of the Code of Federal Regulations and/or the Declaration of Helsinki. The Principal Investigator is responsible for personally overseeing the treatment of all study patients. The Principal Investigator must assure that all study site personnel, including sub-investigators and other study staff members, adhere to the study protocol and all FDA/GCP/NCI regulations and guidelines regarding clinical trials both during and after study completion.

The Principal Investigator at each institution or site will be responsible for assuring that all the required data will be collected and entered onto the Case Report Forms. Periodically, monitoring visits will be conducted and the Principal Investigator will provide access to his/her original records to permit verification of proper entry of data. At the completion of the study, all case report forms will be reviewed by the Principal Investigator and will require his/her final signature to verify the accuracy of the data.

### 13.0 APPENDICES

#### 13.1 Appendix A: Reader Study Data Collection Form

Specimen: \_\_\_\_\_

Reader: \_\_\_\_\_

Date: \_\_\_\_\_

#### Overall Assessment:

##### Acoustic Angiography

Overall specimen malignancy score (-2 to +2): \_\_\_\_\_

Malignancy confidence (0-100) \_\_\_\_\_%

##### ULTRASOUND

Overall specimen malignancy score (-2 to +2): \_\_\_\_\_

Malignancy confidence (0-100) \_\_\_\_\_%

#### 1. Acoustic Angiography versus ULTRASOUND Shape/Morphology

|    |  |
|----|--|
| +3 | I am significantly more confident in the Acoustic Angiography representation of the lesion shape/morphology I described as compared to ULTRASOUND representation of the same lesion      |
| +2 | I am more confident in the Acoustic Angiography representation of the lesion shape/morphology I described as compared to ULTRASOUND representation of the same lesion                    |
| +1 | I am slightly more confident in the Acoustic Angiography representation of the lesion shape/morphology I described as compared to the ULTRASOUND representation of the same lesion.      |
| 0  | I have the same confidence in the Acoustic Angiography representation of the lesion shape/morphology I described as I do in the ULTRASOUND representation of the same lesion             |
| -1 | I am slightly less confident in the Acoustic Angiography representation of the lesion shape/morphology I described as compared to the ULTRASOUND representation of the same lesion.      |
| -2 | I am less confident in the Acoustic Angiography representation of the lesion shape/morphology I described as compared to the ULTRASOUND representation of the same lesion.               |
| -3 | I am significantly less confident in the Acoustic Angiography representation of the lesion shape/morphology I described as compared to the ULTRASOUND representation of the same lesion. |

